## 7.5. BASELINE

Baseline, is defined as the last non-missing measurement (including unscheduled assessment) taken prior to dosing. In the case where the last non-missing measurement and the reference start date coincide, that measurement will be considered baseline.

## 7.6. RETESTS, UNSCHEDULED VISITS AND EARLY TERMINATION DATA

In general, for by-visit summaries, data recorded at the nominal visit will be presented. In the case of a retest, an unscheduled assessment will be created.

Unscheduled measurements (unless assigned to a planned visit number, as stated above) will not be included in by-visit summaries.

Early treatment termination data will not be included in by-visit table summaries and by-visit graphs.

Listings will include scheduled, unscheduled, retest and early discontinuation data collected in the electronic Case Report Form (e-CRF) database.

## 7.7. COMMON CALCULATIONS

For quantitative measurements, change from baseline will be calculated as:

- Test Value (after baseline) – Baseline Value

## 7.8. SOFTWARE VERSIONS

All derivations, statistical analyses, summaries and listings provided by [REDACTED] will be generated using SAS version 9.4 or higher ([REDACTED]). Non-compartmental pharmacokinetic parameter calculations will be performed using Phoenix® WinNonlin® 8.1 or higher ([REDACTED]) and SAS version 9.4 or higher. Table, listing and figures will be prepared using the same versions of SAS.

# 8. STATISTICAL CONSIDERATIONS

## 8.1. MISSING DATA

Missing safety data will not be imputed.

Missing PK concentrations will be handled as described in Section 17.1.2 of this analysis plan.

Document: BI\_1297-0015\_SAP\_Final\_v1.0  
Author: [REDACTED]

Version Number: Final 1.0  
Version Date: 30Sep2022

Template No: CS\_TP\_BS016 – Revision 7  
Effective Date: 01Nov2021

Reference: CS\_WI\_BS005

---

## 9. OUTPUT PRESENTATIONS

APPENDIX 1 shows conventions for presentation of data in outputs.

The templates provided with this TSAP describe the presentations for this study and therefore the format and content of the summary tables, figures and listings to be provided by [REDACTED] Biostatistics.

## 10. DISPOSITION AND WITHDRAWALS

All subjects who provide informed consent will be accounted for in this study. Subject disposition will be tabulated for each study treatment and for all subjects overall with the number of subjects who are screened, screen failure (defined as withdrawn from trial prior to randomization), randomized, randomized but not treated, completed treatment (assessed at Day 1), completed the trial (assessed at Day 57), prematurely discontinue, reason for early discontinuation, entered safety follow-up, completed safety follow-up, discontinue from safety follow-up and reason for early discontinuation from safety follow-up. A listing will present dates of completion or early withdrawal and the reason for early discontinuation, if applicable, for each subject.

A summary table will be produced with the number and percentage of subjects in each analysis sets.

Protocol violations relevant for primary PK analysis (as defined in section 6.4) will be presented for the RND set.

In addition, subject disposition by country and by age groups will be reported overall and will be displayed for ENR population for disclosure purpose.

The following age groups will be reported:

- 18 - 64 years
- 65 - 84 years

## 11. DEMOGRAPHIC AND OTHER BASELINE CHARACTERISTICS

Individual subject demographics and baseline characteristics will be presented for the RND, SAF and PKS. If RND is equivalent to SAF, tables will be displayed for RND only. Otherwise, both populations will be considered. In the same manner, tables will be repeated for PKS only if PKS is not equivalent to RND.

Demographic and other baseline characteristics such as age, sex, childbearing status, race, ethnicity, height, weight, body mass index (BMI), smoking status and alcohol status will be summarized and tabulated by treatment and for all subjects overall. Descriptive statistics will be presented for age, height, weight, and BMI. Frequency counts and percentages will be presented for sex, childbearing status, race, ethnicity, smoking status and alcohol status. No statistical testing will be carried out for demographic or other baseline characteristics.

---

Document: BI\_1297-0015\_SAP\_Final\_v1.0  
Author: [REDACTED]

Version Number: Final 1.0  
Version Date: 30Sep2022

Template No: CS\_TP\_BS016 – Revision 7  
Effective Date: 01Nov2021

Reference: CS\_WI\_BS005

---

## 12. PROTOCOL DEVIATIONS

### 12.1. DEVIATIONS RELATED TO STUDY CONDUCT

A deviation from a protocol occurs when Investigator site staff or a study subject does not adhere to the protocol's stipulated requirements, whether inadvertently or planned. Protocol deviations will be listed including a classification of minor or major and important or not important as determined by clinical staff. A summary table will be produced for protocol deviations relevant for PK evaluation.

Important protocol deviations will be reviewed also by the study pharmacokineticist and biostatistician prior to unblinding to identify deviations which have the potential to affect the pharmacokinetic results.

### 12.2. DEVIATIONS RELATED TO PK ANALYSIS

Changes to the procedures or events, which may impact the quality of the PK data, will be considered significant protocol deviations and will be described within the clinical study report body text. These changes or events will include any circumstances that will alter the evaluation of the PK. Examples include, but may not be limited to, sample processing errors that lead to inaccurate bioanalytical results, and/or inaccurate dosing on the day of PK sampling. In the case of a significant protocol deviation or event, PK data collected during the affected treatment period will be excluded from the study results. Other changes to the procedures or events which do not impact the quality of the PK data will not be considered significant protocol deviations. A common example of a non-significant protocol deviation is a missed blood sample or deviations from blood collection times.

## 13. SURGICAL AND MEDICAL HISTORY

Surgical and Medical History coded using MedDRA Version 25.0 will be presented for the safety analysis set.

Surgical and Medical history will be listed and summarized by SOC and preferred term for each treatment and all subjects overall.

## 14. MEDICATIONS

Medication usage coded using the WHO Drug Dictionary Version March 2022 will be presented for the safety analysis set.

No Anatomical Therapeutic Chemical (ATC) class coding will be performed. The medical terms will be summarized by generic medication name. The generic medication name will be sorted by decreasing

---

Document: BI\_1297-0015\_SAP\_Final\_v1.0  
Author: [REDACTED]

Version Number: Final 1.0  
Version Date: 30Sep2022

Template No: CS\_TP\_BS016 – Revision 7  
Effective Date: 01Nov2021

Reference: CS\_WI\_BS005

frequencies.

- ‘Prior’ medications are medications which started and stopped prior to the single dose of study medication.
- ‘Concomitant’ medications are medications which were ongoing at the time of administration or started during the trial (until end of trial date on Day 70).

See APPENDIX 2 for handling of partial dates for medications, in the case where it is not possible to define a medication as prior or concomitant, the medication will be classified by the worst case; i.e. concomitant.

## 15. STUDY MEDICATION EXPOSURE

The number of subjects receiving study medication will be reported for the SAF.

A listing will be created with the randomisation number and study medication injection details.

## 16. SAFETY OUTCOMES

All outputs for safety outcomes will be based on the Safety Analysis Set.

There will be no statistical comparisons between the treatment groups for safety data, unless otherwise specified with the relevant section.

## 16.1. ADVERSE EVENTS

Adverse Events (AEs) will be coded using Medical Dictionary for Regulatory Activities (MedDRA) central coding dictionary, Version 25.0 or higher. SOCs will be sorted by internationally agreed European Medicines Agency (EMA) SOC order (refer to APPENDIX 3), PTs will be sorted by decreasing frequencies (within system organ class).

In case of worsening in severity, a new entry is created with start date equal to start of worsening.

TEAEs are defined as AEs that started or worsened in severity on or after the single dose of trial medication up to 10 weeks (70 days) post dose.

See APPENDIX 2 for handling of partial dates for AEs. In case it is not possible to define an AE as treatment emergent or not, the AE will be classified by the worst case: i.e. treatment emergent.

An overall summary of number of subjects within each of the categories described in the sub-section below, will be provided as specified in the templates.

Listings will include TEAEs and Non-TEAEs.

Document: BI\_1297-0015\_SAP\_Final\_v1.0  
Author: [REDACTED]

Version Number: Final 1.0  
Version Date: 30Sep2022

Template No: CS\_TP\_BS016 – Revision 7  
Effective Date: 01Nov2021

Reference: CS WI BS005

Copyright © 2009, 2010, 2012, 2016, 2018, 2019, 2021 [REDACTED]. All Rights Reserved. The contents of this document are confidential and proprietary to [REDACTED] Holdings Inc. and its subsidiaries. Unauthorized use, disclosure or reproduction is strictly prohibited.

### **16.1.1. ALL TEAEs**

Incidence of TEAEs will be presented by SOC and PT within each SOC and also broken down further by maximum severity and relationship to trial medication.

#### **16.1.1.1 Intensity**

Intensity is classed as mild/ moderate/ severe (increasing severity). TEAEs starting after the single dose of trial medication with a missing intensity will be classified as severe. If a subject reports a TEAE more than once within that SOC/ PT, the AE with the worst case intensity will be used in the corresponding intensity summaries.

#### **16.1.1.2 Relationship to Trial Medication**

A related TEAE is defined as a TEAE with a causal relationship between the event and the trial drug ticked "Related" according to the investigator. TEAEs with a missing relationship to study medication will be regarded as related to trial medication. If a subject reports the same AE more than once within that SOC/ PT, the AE with the worst case relationship (TEAE with a causal relationship between the event and the trial drug ticked "Related") to trial medication will be used in the corresponding relationship summaries.

### **16.1.2. SERIOUS ADVERSE EVENTS**

Serious adverse events (SAEs) are those events recorded as "Serious" on the Adverse Events page of the eCRF. A summary of serious TEAEs by SOC and PT will be prepared. All SAEs as recorded in the eCRF will be listed.

### **16.1.3. ADVERSE EVENTS LEADING TO DEATH**

TEAEs leading to Death are those events which are recorded as "Results in death" on the Adverse Events page of the eCRF. A summary of subjects with TEAEs leading to death will be presented in overview summary. All AEs leading to Death as recorded in the eCRF will be listed.

### **16.1.4. ADVERSE EVENTS OF SPECIAL INTEREST (AESI)**

An overall summary of the number of subjects and percentages within each of the categories described in the sub-sections below will be provided.

#### **16.1.4.1 Reported by Investigator**

AESI reported by investigators are those events recorded as "Adverse Event of Special Interest" equal to "Yes" on the Adverse Events page of the eCRF.

Document: BI\_1297-0015\_SAP\_Final\_v1.0  
Author: [REDACTED]

Version Number: Final 1.0  
Version Date: 30Sep2022

Template No: CS\_TP\_BS016 – Revision 7  
Effective Date: 01Nov2021

Reference: CS\_WI\_BS005

Number of subjects, percentages and number of events of Treatment Emergent AESI reported by investigators by SOC and PT table will be prepared.

#### 16.1.4.2 Serious Infections

Infections are those events with a SOC equal to "Infections and infestations".

Serious infections are:

- AEs which are both infections and SAEs as reported on the Adverse Events page of the eCRF.
- AEs which are both infections and identified by medical advisor as requiring class IV (intravenous) antibiotics.

Serious infections events of special interest are those events both identified as serious infections adverse events and recorded as "Adverse Event of Special Interest" equal to "Yes" on the Adverse Events page of the eCRF.

Number of subjects, percentages and number of events of Treatment Emergent Infections by SOC and PT tables will be prepared.

Number of subjects, percentages and number of events of Treatment Emergent Serious Infections by SOC and PT tables overall will be prepared.

Serious Infections will be listed. The listing will include the "Adverse Event of Special Interest" equal to "Yes" and the "Is the AE an infection?" equal to "Yes" information from the Adverse Events page of the eCRF as flags.

#### 16.1.4.3 Hypersensitivity Reactions

Hypersensitivity reactions adverse events are those events recorded as MedDRA code in the pre-defined Standardized MedDRA Queries (SMQ) "Hypersensitivity" (narrow).

Hypersensitivity reactions adverse events of special interest are those events both identified as Hypersensitivity reactions adverse events and recorded as "Adverse Event of Special Interest" equal to "Yes" on the Adverse Events page of the eCRF.

Number of subjects, percentages and number of events of Treatment Emergent Hypersensitivity reactions by SOC and PT tables will be prepared.

Hypersensitivity reactions will be listed. The listing will include the "Adverse Event of Special Interest" equal to "Yes" information from the Adverse Events page of the eCRF as a flag.

#### 16.1.4.4 Drug Induced Liver Injury (DILI)

Drug Induced Liver Injury (DILI) are those events identified by medical advisor on the subset of AEs for subjects presenting laboratory potential DILI findings (refer to section 16.3.1).

DILI events of special interest are those events both identified as DILI adverse events and recorded as

Document: BI\_1297-0015\_SAP\_Final\_v1.0  
Author: [REDACTED]

Version Number: Final 1.0  
Version Date: 30Sep2022

Template No: CS\_TP\_BS016 – Revision 7  
Effective Date: 01Nov2021

Reference: CS\_WI\_BS005

"Adverse Event of Special Interest" equal to "Yes" on the Adverse Events page of the eCRF.

Number of subjects, percentages and number of events of Treatment Emergent DILI by SOC and PT tables will be prepared.

DILI will be listed. The listing will include the "Adverse Event of Special Interest" equal to "Yes" information from the Adverse Events page of the eCRF as a flag.

#### 16.1.4.5 Injection-site Reactions

Injection-site reactions are those events recorded within the following subsearches of the BlcMQ "Administration site reactions" (narrow):

- Administration site reactions NEC (subsearch 1)
- Application and instillation site reactions (subsearch 2)
- Injection site reactions (subsearch 5)

Number of subjects, percentages and number of events of Treatment Emergent Injection-site reactions by SOC and PT tables will be prepared.

Injection-site reactions will be listed.

#### 16.1.4.6 Anaphylactic Reactions

Anaphylactic reactions are those events recorded as MedDRA code in the pre-defined SMQ = "Anaphylactic reactions" (narrow).

Anaphylactic reactions adverse events of special interest are those events both identified as Anaphylactic reactions and recorded as "Adverse Event of Special Interest" equal to "Yes" on the Adverse Events page of the eCRF.

Number of subjects, percentages and number of events of Treatment Emergent Anaphylactic reactions by SOC and PT tables will be prepared.

Anaphylactic reactions will be listed. The listing will include the "Adverse Event of Special Interest" equal to "Yes" information from the Adverse Events page of the eCRF as a flag.

### 16.1.5. NON-SERIOUS TREATMENT EMERGENT AEs

Non-serious TEAEs are those events for which the investigator ticked "No" to the item "Is this a serious adverse event?" on the Adverse Events page of the eCRF.

Frequency of subjects, number of events and incidence of subject with non-serious TEAEs will be presented by SOC and PT, if preferred term total incidence >5%.

Document: BI\_1297-0015\_SAP\_Final\_v1.0  
Author: [REDACTED]

Version Number: Final 1.0  
Version Date: 30Sep2022

Template No: CS\_TP\_BS016 – Revision 7  
Effective Date: 01Nov2021

Reference: CS\_WI\_BS005

#### 16.1.6. OTHER SIGNIFICANT AEs

Other significant AEs are not applicable in this single-dose trial as discontinuation, withdrawal or dose reduction cannot happen.

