3.3.4 Withdrawal of subjects from treatment or assessments

Subjects may withdraw or may be removed from trial treatment or may withdraw consent to trial participation as a whole ('withdrawal of consent') with very different implications; please see Sections [3.3.4.1](#) and [3.3.4.2](#) below.

If a subject is removed from or withdraws from the trial prior to the first administration of trial medication, the data of this subject will not be entered in the case report form (CRF) and will not be reported in the clinical trial report (CTR).

If a subject is removed from or withdraws from the trial after the first administration of trial medication, this will be documented and the reason for discontinuation must be recorded in the CRF; in addition, trial data will be included in the CRF and will be reported in the CTR.

Following removal or withdrawal, a complete end-of-trial examination should be performed. If the discontinuation or withdrawal occurs before the end of the REP (see Section [1.2.1](#), the discontinued subject should, if possible, be questioned for AEs and concomitant therapies at or after the end of the REP, in order to ensure collection of AEs and concomitant therapies throughout the REP, if not contrary to any consent withdrawal of the subject.

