3.3.5 Replacement of subjects

In case more than 10 subjects do not complete the trial (including subjects non- evaluable for PK), additional subjects may be recruited and treated with the respective treatment if considered necessary to reach the objective of the trial. Subjects who withdraw or are withdrawn from treatment or assessments because of a drug-related adverse event will not be replaced and no additional subject will be recruited in such a case. The Clinical Trial Leader together with the Trial Pharmacokineticist and the Trial Statistician are to decide, if and how many subjects will be replaced, i.e. recruited in addition. The total number of replacements may not exceed 1/4 of the total number of evaluable subjects anticipated to complete the trial. A replacement subject will be assigned a unique trial subject number, and will be assigned to the same treatment as the subject he or she replaces.

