5.2.4 Electrocardiogram

Twelve-lead ECGs (I, II, III, aVR, aVL, aVF, V1 - V6) will be recorded using a computerised electrocardiograph (i.e. Burdick ELI 150C) at the times provided in the [Flow Chart](#).

To achieve a stable heart rate at rest and to assure high quality recordings, the site personnel will be instructed to assure a relaxed and quiet environment, so that all subjects are at complete rest.

Proprietary confidential information © 2021 Boehringer Ingelheim International GmbH or one or more of its affiliated companies

All ECGs will be recorded for a 10 sec duration after subjects have rested for at least 5 min in a supine position. ECG assessment will always precede all other trial procedures scheduled for the same time to avoid compromising ECG quality.

All ECGs will be stored electronically. Electrode placement will be performed according to the method of Wilson, Goldberger and Einthoven modified by Mason and Likar (hips and shoulders instead of ankles and wrists). Precise electrode placement will be marked with an indelible mark on the skin to allow reproducible placement throughout the trial.

All locally printed ECGs will be evaluated by the investigator or a designee. Abnormal findings will be reported as AEs (during the trial) or baseline conditions (if identified at the screening visit) if assessed to be clinically relevant by the investigator. Any ECG abnormalities will be carefully monitored and, if necessary, the subject will be removed from the trial and will receive the appropriate medical treatment.

ECGs may be repeated for quality reasons (for instance, due to alternating current artefacts, muscle movements, or electrode dislocation) and the repeated ECG will be used for analysis. Additional (unscheduled) ECGs may be collected by the investigator for safety reasons.

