7.2.5 Safety analyses

Safety will be analysed based on the assessments described in Section [2.2.2.2](#). All treated subjects (TS, refer to Section [7.2](#)) will be included in the safety analysis. Safety analyses will be descriptive in nature and based on BI standards. No hypothesis testing is planned.

For all analyses, the treatment actually administered (= treatment at onset) to the subject will be used (any deviations from the randomised treatment will be discussed at the Report Planning Meeting).

Treatments will be compared in a descriptive way. Tabulations of frequencies/proportions will be used to evaluate categorical (qualitative) data, and tabulations of descriptive statistics will be used to analyse continuous (quantitative) data.

Adverse events will be coded using the Medical Dictionary for Regulatory Activities (MedDRA). All events with an onset after the first dose of trial medication up to a period of 10 weeks after the last dose of the trial medication (i.e., end of the REP) will be assigned to the treatment phase for evaluation, and will be referred to as treatment emergent adverse events (TEAEs). Frequency, intensity and causal relationship of AEs will be tabulated by treatment, primary system organ class and preferred term. SAEs and other significant AEs (according to ICH E3), and protocol-specified AESIs (see Section [5.2.6.1](#)), will be listed separately.

Proprietary confidential information © 2021 Boehringer Ingelheim International GmbH or one or more of its affiliated companies

The number and percentage of subjects with injection site reactions (assessed at Day 1 from the time of the injection until Day 2, prior to discharge from the trial site) will be summarized by treatment for each injection site reaction.

Previous and concomitant therapies will be presented per treatment group without consideration of time intervals and treatment periods.

Laboratory values taken after the first dose of trial medication up to a period of 10 weeks after the last dose of the trial medication will be assigned to the treatment phase for evaluation. Descriptive statistics of laboratory values over time and for the change from baseline will be provided for each treatment group. Laboratory parameters will be compared to their reference ranges and frequency tables will be provided for the number of subjects within and outside the reference range.

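### The SAP drops the planned listing of other significant AEs on a premise both documents contradict, and its DILI laboratory rule is narrower than the protocol's AESI definition

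*SAP*

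**What the plan says.** **Other significant AEs.** Protocol 7.2.5 commits to listing "SAEs and other significant AEs (according to ICH E3), and protocol-specified AESIs" separately. SAP 16.1.6 answers with one sentence: "Other significant AEs are not applicable in this single-dose trial as discontinuation, withdrawal or dose reduction cannot happen". SAP 4.3 reports no departure from the protocol's planned analyses.

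Other sections provide for leaving the trial after dosing:

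- Protocol 3.3.4: "If a subject is removed from or withdraws from the trial after the first administration of trial medication, this will be documented". The reason goes into the CRF.
- Protocol 3.3.5 sets a replacement rule for "Subjects who withdraw or are withdrawn from treatment or assessments because of a drug-related adverse event".
- Protocol 5.2.4, on ECG abnormalities: "if necessary, the subject will be removed from the trial".
- SAP 10 includes "prematurely discontinue, reason for early discontinuation" in the disposition table and adds: "A listing will present dates of completion or early withdrawal and the reason for early discontinuation, if applicable, for each subject".

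**DILI.** Protocol 5.2.6.1.4 defines potential severe DILI as AST and/or ALT of at least 3×ULN combined with total bilirubin of at least 2×ULN, in one sample or in samples no more than 30 days apart, or else ALT and/or AST of at least 10×ULN. In SAP 16.3.1, DILI Category 1 takes the combined finding only when both values come from one sample. Category 2 is the 10×ULN limb. A 30-day window appears only in Hy's law Category 2, and only for bilirubin following the transaminase peak. SAP 16.3 reports the incidence of possible DILI. SAP 16.1.4.4 selects DILI events among subjects with laboratory findings under 16.3.1.

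**The concern.** The reason given in SAP 16.1.6 is true of the dose and untrue of trial participation. An AE that makes a subject leave follow-up is the kind of event that section ties to discontinuation and withdrawal, yet the SAP text plans no dedicated display of it. The two formulations are compared only descriptively for safety, so the displays are the comparison. Without the listing, identifying AEs that led to exit means matching the withdrawal listing to the AE listing by hand.

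On DILI, the laboratory incidence can undercount subjects who meet the protocol's own AESI laboratory definition. There is also a downstream effect. A case correctly flagged by the investigator would appear in the investigator-reported AESI table (SAP 16.1.4.1), yet could be absent from the DILI table and listing in 16.1.4.4.

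**Working it through.** **Part 1: comparison of text.** No arithmetic applies.

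| Event named in SAP 16.1.6 | Possible after the single dose? |
|---|---|
| Dose reduction | No |
| Discontinuation of treatment | No, the one dose has been given |
| Withdrawal from the trial or its assessments | Yes: protocol 3.3.4, 3.3.5, 5.2.4; SAP 10 |

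The third row defeats the stated reason. Protocol 7.2.5 leaves details of safety presentation to the TSAP, but removing a listing that the same section promises is more than a detail. SAP 4.3 is therefore inaccurate on this item.

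**Part 2: pattern count.** Take two samples no more than 30 days apart. Each has ALT/AST in one of three bands (<3, 3 to <10, ≥10×ULN) and bilirubin in one of two (<2, ≥2×ULN). That gives 3 × 2 = 6 states per sample and 6 × 6 = 36 ordered patterns.

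- At least one sample with ALT/AST ≥10×ULN: 36 − 4 × 4 = 20.
- None ≥10×ULN, but at least one sample with ALT/AST of 3 to <10×ULN and bilirubin ≥2×ULN together: 4 × 4 − 3 × 3 = 7.
- Neither of these, but the two findings fall in different samples: 2 (one for each order).

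| Rule | Patterns met |
|---|---|
| Protocol 5.2.6.1.4 | 20 + 7 + 2 = 29 |
| SAP DILI Categories 1 and 2 | 20 + 7 = 27 |
| SAP DILI or Hy's law categories | 27 + 1 = 28 |

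Hy's law Category 2 recovers the order ALT/AST first, then bilirubin. No SAP category recovers the reverse order. SAP 16.1.4.4 refers to 16.3.1 as a whole and does not say whether the Hy's law categories count, so its AE subset misses 1 or 2 patterns.

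**Can it occur on scheduled post-dose visits?** Enzymes are measured on Days 10, 22 and 57. The windows in protocol 6.1 are ±2 hours at Day 10 and ±1 day at Days 22 and 57.

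- Day 10 to 22: 12 days, range 10.9 to 13.1. Inside 30 days.
- Day 22 to 57: 35 days, range 33 to 37. Outside.
- Day 10 to 57: 47 days, range 45.9 to 48.1. Outside.

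If total bilirubin belongs to panel B, one day pair (10/22) qualifies. If it belongs only to panel D, none does. The available text of Table 5.2.3:1 is broken and does not settle which.

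For illustration, assume ALT of 4×ULN and bilirubin of 2.5×ULN:

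| Sequence | Protocol AESI | SAP DILI | SAP Hy's law |
|---|---|---|---|
| Same sample | Yes | Yes | Yes |
| ALT Day 10, bilirubin Day 22 | Yes | No | Yes |
| Bilirubin Day 10, ALT Day 22 | Yes | No | No |

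Whatever the panel, protocol 6.2.3 requires clinically relevant abnormal values to be followed with further tests. That can create unscheduled pairs within 30 days; their number cannot be estimated from the documents.

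**The case against.** SAP 16.1.6 can be read as speaking of treatment only: it refers to a single-dose trial, SAP 10 counts treatment as completed on Day 1, and the protocol separates stopping treatment from withdrawing consent. The ICH E3 definition is not reproduced, so whether it covers exit from assessments cannot be read from the documents. SAP 10 already tabulates reasons for discontinuation by treatment, and SAP 9 says "The templates provided with this TSAP describe the presentations for this study"; those templates are not available here and might contain the link between event and exit.

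On DILI, the laboratory incidence is an addition by the SAP, and the protocol does not require it to reproduce the AESI definition. Investigator-flagged AESIs are tabulated independently of 16.3.1, scatter plots of ALT and AST against bilirubin are planned, and all laboratory data are listed. The pattern counts weight a constructed grid equally and measure no rate.

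Much of this limits the impact, and none of it removes the point. The treatment-only reading fails against protocol 3.3.5, which names withdrawal from assessments because of a drug-related AE. No outside definition is needed, because 16.1.6 itself ties the category to discontinuation and withdrawal. A tabulated reason does not identify the AE. It is accepted that the DILI part is a mismatch of definitions and not an undeclared change. Same-sample wording also occurs in protocol 3.3.4.1, criterion 5; that is a withdrawal rule, not the AESI definition, and no claim is made on it.

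**Conclusion.** Both parts hold, as a minor point. SAP 16.1.6 removes a planned listing for a reason that the protocol and SAP 10 contradict, and SAP 4.3 does not declare it. SAP 16.3.1 omits one sequence that meets the AESI definition from every laboratory category, and two sequences from the DILI categories.

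Expected counts are very small, and the documents give no rate for AE-related withdrawal or DILI. The conclusion on part 1 rests on the SAP text, since the templates and eCRF are not shown. On part 2 the difference in definitions is certain. Whether it can arise on scheduled visits depends on the bilirubin panel.

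**What to change.** 1. Replace SAP 16.1.6 with a listing by treatment of TEAEs that led to withdrawal from the trial or its assessments. Alternatively, declare the removal in SAP 4.3 with a justification that holds for trial exit.
2. Reword DILI Category 1 in SAP 16.3.1 to follow protocol 5.2.6.1.4: AST and/or ALT ≥3×ULN with total bilirubin ≥2×ULN, in one sample or in two samples no more than 30 days apart, in either order. Use it for the DILI incidence in 16.3.
3. State in SAP 16.1.4.4 which 16.3.1 categories define the AE subset.

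The cost is SAP wording before database lock, one listing and one derivation. Reasons for discontinuation and laboratory values are already collected. If the eCRF does not link a specific AE to the exit, the match can be made at the report planning meeting before unblinding.
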